9.1 Overall Study Design and Plan Description**Table 1: Study Design**

| Arm | Sample Size | First Vaccination | Second Vaccination | | Third Vaccination | |
|-----|-------------|--|--------------------|--|-------------------|----------------------|
| | | Product and Dose | Interval | Product and Dose | Interval | Product and Dose |
| 2A | 15 | 100 mcg mRNA-1273 | 28 days | 100 mcg mRNA-1273 | 28 days | 50 mcg mRNA-1273.351 |
| 2B | 15 | 50 mcg mRNA-1273 | 28 days | 50 mcg mRNA-1273 | 28 days | 50 mcg mRNA-1273.351 |
| 2C | 20 | 100 mcg mRNA-1273.351 | 28 days | 100 mcg mRNA-1273.351 | | None |
| 2D | 20 | 50 mcg mRNA-1273.351 | 28 days | 50 mcg mRNA-1273.351 | | None |
| 2E | 20 | 100 mcg mRNA-1273 | 28 days | 100 mcg mRNA-1273.351 | | None |
| 2F | 20 | 50 mcg mRNA-1273 | 28 days | 50 mcg mRNA-1273.351 | | None |
| 2G | 20 | 50 mcg mRNA-1273 + 50 mcg mRNA-1273.351 | 28 days | 50 mcg mRNA-1273 + 50 mcg mRNA-1273.351 | | None |
| 2H | 20 | 25 mcg mRNA-1273 + 25 mcg mRNA-1273.351 | 28 days | 25 mcg mRNA-1273 + 25 mcg mRNA-1273.351 | | None |

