14.2 Immunogenicity Data

Table 15: Serum IgG Binding Assay Arbitrary Units/mL Measured by ECLIA Geometric Mean Results with 95% Confidence Intervals by Time Point and Treatment Group, S-2P-Wa-1 – mITT Population, Treatment Arms 2A-B (Three Vaccinations)

| Planned Time Point | Statistic | Arm 2A (N=X) | Arm 2B (N=X) | All Subjects |
|--------------------|-----------|-----------------|-----------------|--------------|
| Day 1, Pre-Dose | n | | | |
| | GM | | | |
| | 95% CI | | | |
| Day 15 | n | | | |
| | GM | | | |
| | 95% CI | | | |
| Day 29 | n | | | |
| | GM | | | |
| | 95% CI | | | |
| Day 43 | n | | | |
| | GM | | | |
| | 95% CI | | | |
| Day 57 | n | | | |
| | GM | | | |
| | 95% CI | | | |
| Day 71 | n | | | |
| | GM | | | |
| | 95% CI | | | |
| Day 85 | n | | | |
| | GM | | | |

| Planned Time Point | Statistic | Arm 2A (N=X) | Arm 2B (N=X) | All Subjects |
|--------------------|-----------|-----------------|-----------------|--------------|
| | 95% CI | | | |
| Day 147 | n | | | |
| | GM | | | |
| | 95% CI | | | |
| Day 237 | n | | | |
| | GM | | | |
| | 95% CI | | | |
| Day 422 | n | | | |
| | GM | | | |
| | 95% CI | | | |
| Peak GM | n | | | |
| | GM | | | |
| | 95% CI | | | |

Notes: N=Number of subjects in the mITT population.
n=Number of subjects with results available at time point.
GM=Geometric Mean, NE=Not Estimable.
Confidence intervals of the geometric means were calculated with the Student's t distribution on log-transformed data.

Tables with Similar Format:

Implementation notes:

For tables using the PP population, update footnote to read: “Notes: N=Number of subjects in the Per Protocol population.”

For all AUC tables, add footnote reading: “Geometric Mean is calculated as the Williams mean using log(1+x).”

| | |
|------------------|---|
| Table 16: | Serum IgG Binding Assay Arbitrary Units/mL Measured by ECLIA Geometric Mean Results with 95% Confidence Intervals by Time Point and Treatment Group, S-2P–Wa-1 – Per Protocol Population, Treatment Arms 2A-B (Three Vaccinations) |
| Table 17: | Serum IgG Binding Assay Arbitrary Units/mL Measured by ECLIA Geometric Mean Results with 95% Confidence Intervals by Time Point and Treatment Group, RBD–Wa-1 – mITT Population, Treatment Arms 2A-B (Three Vaccinations) |

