- Table 399: Summary of Solicited Events by Days Post Dose 2, Symptom, and Treatment Group – Treatment Arm 2D (Two Vaccinations)**
- Table 400: Summary of Solicited Events by Days Post Dose 1, Symptom, and Treatment Group – Treatment Arm 2E (Two Vaccinations)**
- Table 401: Summary of Solicited Events by Days Post Dose 2, Symptom, and Treatment Group – Treatment Arm 2E (Two Vaccinations)**
- Table 402: Summary of Solicited Events by Days Post Dose 1, Symptom, and Treatment Group – Treatment Arm 2F (Two Vaccinations)**
- Table 403: Summary of Solicited Events by Days Post Dose 2, Symptom, and Treatment Group – Treatment Arm 2F (Two Vaccinations)**
- Table 404: Summary of Solicited Events by Days Post Dose 1, Symptom, and Treatment Group – Treatment Arm 2G (Two Vaccinations)**
- Table 405: Summary of Solicited Events by Days Post Dose 2, Symptom, and Treatment Group – Treatment Arm 2G (Two Vaccinations)**
- Table 406: Summary of Solicited Events by Days Post Dose 1, Symptom, and Treatment Group – Treatment Arm 2H (Two Vaccinations)**
- Table 407: Summary of Solicited Events by Days Post Dose 2, Symptom, and Treatment Group – Treatment Arm 2H (Two Vaccinations)**

Table 408: Summary of Number of Days of Solicited Symptoms by Treatment Group - All Subjects

| Variable | Statistic | Arm 2A (N=X) | Arm 2B (N=X) | Arm 2C (N=X) | Arm 2D (N=X) | Arm 2E (N=X) | Arm 2F (N=X) | Arm 2G (N=X) | Arm 2H (N=X) | All Subjects (N=X) |
|-----------------------------|--------------------|-----------------|-----------------|-----------------|-----------------|-----------------|-----------------|-----------------|-----------------|-----------------------|
| Any Symptom | n | | | | | | | | | |
| | Mean | | | | | | | | | |
| | Standard Deviation | | | | | | | | | |
| | Median | | | | | | | | | |
| | Minimum | | | | | | | | | |
| | Maximum | | | | | | | | | |
| Any Systemic Symptom | n | | | | | | | | | |
| | Mean | | | | | | | | | |
| | Standard Deviation | | | | | | | | | |
| | Median | | | | | | | | | |
| | Minimum | | | | | | | | | |
| | Maximum | | | | | | | | | |
| Arthralgia | n | | | | | | | | | |
| | Mean | | | | | | | | | |
| | Standard Deviation | | | | | | | | | |
| | Median | | | | | | | | | |
| | Minimum | | | | | | | | | |
| | Maximum | | | | | | | | | |
| Fatigue | n | | | | | | | | | |
| | Mean | | | | | | | | | |

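### Arms 2A and 2E, and arms 2B and 2F, receive the same first vaccination, but no planned display estimates that first dose from the 35 subjects available per dose level

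*SAP*

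**What the plan says.** Table 1 of the SAP gives the design. For 100 mcg mRNA-1273 as first vaccination the rows begin "2A | 15 | 100 mcg mRNA-1273 | 28 days" and "2E | 20 | 100 mcg mRNA-1273 | 28 days". For 50 mcg they begin "2B | 15 | 50 mcg mRNA-1273 | 28 days" and "2F | 20 | 50 mcg mRNA-1273 | 28 days". The second vaccination follows after 28 days in every arm. Tables 2 and 3 give the three-dose and two-dose schedules the same contacts up to that point (Days 1, 8, 15 and 29), with the same windows and the same serum draws.

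Solicited events after dose 1 are tabulated one arm at a time. Arms 2A, 2B, 2E and 2F are in Tables 390, 393, 400 and 402, and the last two follow the pattern "Summary of Solicited Events by Days Post Dose 1, Symptom, and Treatment Group – Treatment Arm 2E (Two Vaccinations". The columns of these tables are days, and there is no combined column.

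Immunogenicity is reported in two families of tables. The three-dose family, from Table 15 on, has the columns "Arm 2A (N=X) | Arm 2B (N=X) | All Subjects". The two-dose family, from Table 39 on, has arms 2C to 2H and their total. Both families include Days 15 and 29.

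Section 3.1 makes the frequency and grade of solicited events after each vaccination a primary endpoint. Section 9 plans exact confidence intervals for the proportions reporting them.

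**The concern.** Eight arms give only six different first vaccinations. Until dose 2, arms 2A and 2E are one randomised exposure, and so are 2B and 2F. The separation of 2A-B from 2C-H rests on a third dose due at Day 57, which cannot affect a Day 15 result or a reaction to dose 1.

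The plan therefore reports two smaller-sample results for one product and dose, and no combined estimate. The totals that exist do not fill the gap. In the 2A-B tables the total combines two dose levels of mRNA-1273. In the 2C-H tables it also combines mRNA-1273, mRNA-1273.351 and their mixture. Table 389 shows all eight arms, but section 9.3.1 ties it to the third vaccination and its footnote to all symptoms after dosing. On neither reading is it a dose-1 summary.

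At stake is the precision of the single-dose description of mRNA-1273, which belongs to a primary endpoint.

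**Working it through.** **Inputs.** Arm sizes 15, 15, 20 and 20 from Table 1. Exact binomial intervals from section 9. Student's t intervals on log-transformed titres from section 8.2 and the table footnotes. Detection probabilities from Table 4.

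**The plan's own figures.** The probability of at least one event is 1 − (1 − p)^n.
- p = 20%: n = 15 gives 96.5% and n = 20 gives 98.8%, as in Table 4.
- p = 5%: n = 15 gives 53.7% and n = 20 gives 64.2%, as in Table 4.

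All other n = 15 and n = 20 cells of Table 4 also reproduce.

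**Size by first vaccination received.** 2A + 2E = 15 + 20 = 35, and 2B + 2F = 15 + 20 = 35. Arms 2C, 2D, 2G and 2H stay at 20 each. Check: 35 + 35 + 4 × 20 = 150.

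**Detection at n = 35.**
- p = 5%: 1 − 0.95^35 = 83.4% (53.7% at n = 15, 64.2% at n = 20).
- p = 10%: 1 − 0.90^35 = 97.5% (79.4% and 87.8%).

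**Exact two-sided 95% upper limit with no events**, 1 − 0.025^(1/n):
- n = 15: 21.8%
- n = 20: 16.8%
- n = 35: 10.0%

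**Exact 95% interval at an observed 40%**, which is closer to a common reaction:
- 6/15: 16.3% to 67.7%, width 51 points
- 8/20: 19.1% to 63.9%, width 45 points
- 14/35: 23.9% to 57.9%, width 34 points

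**Log-titre interval.** The half-width is t(0.975, n − 1) / √n, in units of the SD:
- n = 15: 0.554
- n = 20: 0.468
- n = 35: 0.344

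The reduction is 1 − 0.344/0.554 = 38% against n = 15, and 1 − 0.344/0.468 = 27% (unrounded inputs) against n = 20, taking the same SD at each size. The SAP gives no titre SD. If the log10 SD is assumed to lie between 0.3 and 0.5, the limits stand a factor of 1.47 to 1.89 from the geometric mean at n = 15, 1.38 to 1.71 at n = 20, and 1.27 to 1.49 at n = 35.

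**The case against.** The strongest reply is that the SAP contains no error here. Reporting by arm follows the randomisation, and section 6.1 calls for a column per treatment. Section 2.1 describes the purpose in terms of vaccination schedules, and section 5 justifies the sample size per arm. The dose-1 data are shown for every arm by day. The counts for 2A and 2E can be added by hand, a combined geometric mean can be rebuilt from each arm's n, mean and interval, and section 6.5 allows ad hoc analyses. Most of this stands, and it limits the point to a missing supplementary display. It does not remove the value of fixing in advance a grouping that matches exposure. A pooling chosen after the results are seen is open to the charge of having been chosen for them.

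Three caveats also stand:
- The trial is open-label, so reporting may differ slightly between subjects who know they are on different schedules. The by-arm results should stay beside the combined ones.
- Tables 2 and 3 put serum and the second vaccination on the same Day 29 visit, and the SAP does not say in words that blood is drawn first.
- The figure list available stops at Figure 168, so the later solicited-event figures cannot be checked. Section 9.3.1 describes no grouping by first vaccination for them.

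A reader might also infer that the mRNA-1273 first doses are the trial's reference group for the other first doses. The SAP names no reference group and specifies no between-arm comparison.

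**Conclusion.** The point holds as a loss of precision that is cheap to recover. Per dose level of mRNA-1273, 35 planned subjects would support one first-dose estimate, where the plan gives two from 15 and 20. The zero-event upper limit would fall from 21.8% or 16.8% to 10.0%, and the log-titre interval would narrow by 38% or 27%.

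A reader might go further and conclude that the by-arm results are biased or wrong, or that data are discarded. The documents do not support that: each arm's table is a valid estimate, and nothing is lost from the record. Nor are the dose-1 reactogenicity tables pooled over unlike products, since they have no combined column at all.

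The size rests on three assumptions. The Table 1 arm sizes must be reached; section 4.1 allows enrolment to close early, and the ratio printed in section 4.4.3 has seven terms for eight arms. The combined groups may be used only for outcomes before dose 2. The zero-event limit is a convenient illustration; at an observed 40% the interval width goes from 51 or 45 points to 34.

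**What to change.** Keep all by-arm tables, including those after dose 1. Add one post-dose-1 reactogenicity table by first vaccination received, with exact 95% confidence intervals and six columns: 2A+2E (100 mcg mRNA-1273), 2B+2F (50 mcg mRNA-1273), 2C, 2D, 2G and 2H. Use the same six groups for geometric mean, fold rise and seropositivity at Day 15, and at Day 29 for blood drawn before dose 2, with a footnote that says so. One sentence in each of sections 8.2 and 9.3.1 would define the grouping.

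The cost is a few extra tables and no new data. Whether to keep the All Subjects column is a separate layout choice and not part of this point.

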3. STUDY OBJECTIVES AND ENDPOINTS

3.1. Study Objectives and Endpoints

| OBJECTIVES | ENDPOINTS (OUTCOME MEASURES) |
|--|--|
| Primary | |
| 
 To evaluate the safety and reactogenicity of mRNA-1273 and mRNA-1273.351 vaccines, in naïve individuals. | 
 Frequency and grade of each solicited local and systemic reactogenicity AE during a 7-day follow-up period post each vaccination. Frequency and grade of any unsolicited AEs during the 28-day follow-up period post each vaccination. Frequency of any SAEs, Protocol Specified AESIs, NOCMCs, and MAAEs from the first vaccination through 12 months after the last vaccination. |
| Secondary | |
| 
 To assess humoral immunogenicity of mRNA-1273 and mRNA-1273.351 vaccines, in naïve individuals. | 
 Response rate, and magnitude of SARS-CoV-2-specific antibody binding and neutralization titers in serum samples as assessed via a range of assays at all timepoints. |
| Exploratory | |
| 
 To assess, in at least a subset of samples the innate immune response and B cell response following vaccination. | 
 Magnitude, phenotype, and percentage of innate immune cells and SARS-CoV-2 specific B cells, as measured by flow cytometry, and targeted B cell repertoire analysis at different timepoints post vaccination relative to baseline. |
| 
 To assess, in at least a subset of samples, the SARS-CoV-2 S protein-specific T cell responses. | 
 Magnitude, phenotype, and percentage of cytokine producing S protein-specific T cells, as measured by flow cytometry at different timepoints post vaccination relative to baseline. |

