9.2. Measurements of Treatment Compliance

All subjects are to receive 2 (Arms 2C-H) or 3 (Arms 2A-B) doses of study product administered in the clinic. The number of subjects receiving each dose will be summarized as part of the subject disposition table (Table 7 and Table 8).

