9.3.1. Solicited Events and Symptoms

Systemic solicited adverse events were collected pre-vaccination, and systemic and local solicited adverse events were collected 30 minutes post-vaccination and then daily for 7 days after the vaccination and graded on a scale of 0 (absent), 1 (mild), 2 (moderate) and 3 (severe). Systemic events include: fatigue, headache, myalgia, arthralgia, nausea, chills and fever. Local events include: pain at injection site, erythema, and induration.

For each systemic and local event, any systemic event, any local event, and any solicited event, the maximum severity over 7 days after the third vaccination will be summarized for the Safety population. The number and percentage of subjects reporting each event will be summarized by the maximum severity and treatment group (Table 389). For each event the denominator is the number of subjects with non-missing data for the specific event.

The number of subjects reporting a solicited adverse event will be summarized for each day post-vaccination both in a summary table (starting with Table 390 and ending with Table 407) and graphically in a bar chart (Figure 1250, Figure 1251, Figure 1252, Figure 1253, Figure 1254, and Figure 1255).

The mean, standard deviation, median, minimum and maximum duration of solicited events will be summarized (Table 408).

Day of solicited symptom onset will be summarized graphically (Figure 1256, Figure 1257, Figure 1258, Figure 1259, Figure 1260, and Figure 1261).

Solicited adverse events by subject will be presented in listings (Listing 10 and Listing 11) and graphically (starting with Figure 1262 and ending with Figure 1275).

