|--|--------------------|-----------------|-----------------|-----------------|-----------------|-----------------|-----------------|-----------------|-----------------|-----------------------|
| | Minimum | | | | | | | | | |
| | Maximum | | | | | | | | | |
| Induration/swelling | n | | | | | | | | | |
| | Mean | | | | | | | | | |
| | Standard Deviation | | | | | | | | | |
| | Median | | | | | | | | | |
| | Minimum | | | | | | | | | |
| | Maximum | | | | | | | | | |
| Pain | n | | | | | | | | | |
| | Mean | | | | | | | | | |
| | Standard Deviation | | | | | | | | | |
| | Median | | | | | | | | | |
| | Minimum | | | | | | | | | |
| | Maximum | | | | | | | | | |
| Notes: N=Number of subjects in the Safety Population. n=Number of solicited adverse events. | | | | | | | | | | |

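### Table 408 summarises solicited-symptom duration over events with all doses pooled, and does not say how the Any rows are derived

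*SAP*

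**What the plan says.** SAP Section 9.3.1 states that "The mean, standard deviation, median, minimum and maximum duration of solicited events will be summarized" and points to Table 408. The shell, in Appendix 1 under 14.3.1.1, is titled "Summary of Number of Days of Solicited Symptoms by Treatment Group - All Subjects". Its columns are the eight arms and All Subjects. Its rows are Any Symptom, Any Systemic Symptom, Any Local Symptom, seven single systemic symptoms and three single local ones. Each row shows n, mean, SD, median, minimum and maximum. Dose appears neither as a row nor as a column.

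The footnote defines N as the subjects in the Safety Population, but then sets "n=Number of solicited adverse events". Nearby shells keep the two units apart: Tables 409 and 410 define n as events, and Table 411 defines it as subjects.

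Section 9.2 states that "All subjects are to receive 2 (Arms 2C-H) or 3 (Arms 2A-B) doses of study product administered in the clinic". Section 3.1 words the primary reactogenicity endpoint as "Frequency and grade of each solicited local and systemic reactogenicity AE during a 7-day follow-up period post each vaccination".

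**The concern.** Subjects are randomised, and each is vaccinated two or three times. A duration summary taken over events gives a subject as many votes as that subject has events. A few people with many symptoms can then dominate an arm's mean and median, and the SD mixes variation within subjects with variation between them.

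The pooling of doses matters separately. In Arms 2A, 2B, 2E and 2F the product changes between doses, so a pooled duration cannot be assigned to either vaccine, although the primary objective concerns the reactogenicity of both.

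Finally, the Any rows have no stated derivation. Two programmers could fill them from the same shell with materially different numbers.

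**Working it through.** The SAP prints no result for Table 408, so there is no figure to reproduce. The check has four parts.

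**1. How far n can exceed N.** Inputs: 15 subjects and 3 doses in each of Arms 2A-B, 20 subjects and 2 doses in each of Arms 2C-H (Table 1), and 7 systemic plus 3 local single-symptom rows (Table 408). Assume one episode per symptom per dose and, for the Any rows, pooled event durations. Then largest n = subjects × doses × symptoms in the row.

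| Row | 15 subjects, 3 doses | 20 subjects, 2 doses |
|---|---|---|
| Single symptom | 15×3×1 = 45 | 20×2×1 = 40 |
| Any Local | 15×3×3 = 135 | 20×2×3 = 120 |
| Any Systemic | 15×3×7 = 315 | 20×2×7 = 280 |
| Any Symptom | 15×3×10 = 450 | 20×2×10 = 400 |

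Per subject, Any Symptom can hold 3×10 = 30 or 2×10 = 20 entries. In the All Subjects column the limit is 2×450 + 6×400 = 3,300 for N = 150. The 30 three-dose subjects are 20% of N but can supply 900/3,300 = 27% of the entries.

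**2. What pooling doses mixes (Table 1).** Arms 2A and 2B receive mRNA-1273 at doses 1 and 2 and mRNA-1273.351 at dose 3. Arms 2E and 2F receive mRNA-1273 first and mRNA-1273.351 second. By contrast, Section 9 summarises solicited severity for each dose, and the day-by-day Tables 390-407 are split by arm and dose.

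**3. Pooled event mean against days with any symptom, by hand.**

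- One subject after one dose has pain on days 1-3, fatigue on day 2 and headache on days 3-4. Event mean = (3+1+2)/3 = 2.0 days; days with any symptom = 4. Within one subject and dose, the event mean can never exceed the days with any symptom, because no single symptom outlasts the combined period.
- Across subjects the direction can reverse. Subject A has one symptom for 1 day; subject B has five fully overlapping symptoms for 3 days. Event mean = (1 + 5×3)/6 = 2.67; subject mean = (1+3)/2 = 2.0.

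**4. The same comparison by simulation.** All inputs are assumptions, since the SAP gives none: 15 subjects, 3 doses, 10 symptoms, a 7-day window, onset on day 1 or 2, and 400 runs per setting. A subject factor shifts both the chance of a symptom and its chance of continuing to the next day.

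| Setting (symptom probability; daily continuation; SD of the subject factor on each, logit scale) | Event mean | Mean days with any symptom | Runs with event mean lower |
|---|---|---|---|
| 0.40; 0.5; 0 and 0 | 1.99 | 3.82 | 100% |
| 0.40; 0.5; 1 and 0.5 | 2.30 | 4.05 | 100% |
| 0.40; 0.5; 2 and 1.5 | 3.40 | 4.50 | 98% |
| 0.15; 0.5; 2.5 and 2.5 | 4.78 | 4.79 | 54% |
| 0.10; 0.3; 3 and 3 | 4.64 | 4.60 | 48% |

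The shortfall is 48%, 43% and 24% in the first three settings (1 − 1.99/3.82, 1 − 2.30/4.05, 1 − 3.40/4.50). It disappears in the last two, which combine rarer symptoms with extreme differences between subjects.

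**The case against.** Event-level duration answers a legitimate question: how long a headache lasts when it occurs. Section 9.3.1 announces the duration of events, which fits the footnote. The primary endpoint is frequency and grade, so duration is supplementary. Tables 390-407 already give daily counts for each arm and dose. Summing the Any Symptom counts over Days 1-7 and dividing by N yields mean symptomatic days within that window. Sections 9 and 9.3.1 also list any local, any systemic and any solicited event beside the single events for severity. If the Any rows of Table 408 are meant as composites of that kind, only the footnote is wrong.

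Much of this stands, and it limits the point. It does not remove the pooling of doses, and it does not supply the missing derivation. The daily tables allow a mean to be worked out, but not the SD, median or range, and they collapse everything from Day 8 onwards. The once-per-subject rule in Section 9.3 is written for incidence and does not settle the unit for duration.

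A reader might go further and infer three things that the SAP does not support:

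- **That the Any Symptom duration is understated.** The derivation is not given. Even under pooling the direction is not fixed, as the 2.67 against 2.0 example shows.
- **That the arms with most reactions are understated most.** Weighting towards subjects with many symptoms can pull the other way, and nothing here compares arms.
- **That repeated events give false precision, poor coverage or inflated type I error.** Table 408 carries no standard error, interval or test, so there is nothing planned for such rates to attach to. An SD over events describes events and assumes no independence.

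**Conclusion.** The point holds as a fault in unit and definition. By its footnote, Table 408 is taken over events and, by its layout, over all doses together. Its n can reach 45 or 40 in a single-symptom row. If event durations are pooled, it can reach 450 or 400 in Any Symptom, for arms of 15 or 20 subjects. In four of the eight arms the pooled duration cannot be tied to one vaccine. The derivation of the Any rows is missing. If events are pooled, as the footnote implies, understatement of symptomatic days is likely but not certain, and its size depends on assumed symptom rates and durations.

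This is a cheap improvement. The table is descriptive and duration is not itself an endpoint, but it is the only duration table that Section 9.3.1 cites within the primary safety domain.

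**What to change.** In Table 408 and Section 9.3.1:

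1. Present the summary by dose: Dose 1, Dose 2 and, for Arms 2A-B, Dose 3.
2. Use one value per subject per dose, and redefine n in the footnote as the number of subjects reporting the symptom after that dose. It is then at most 15 per dose in each of Arms 2A-B and 20 in each of Arms 2C-H.
3. For Any Symptom, Any Systemic Symptom and Any Local Symptom, define duration as the number of days with at least one qualifying symptom for that subject after that dose.

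The cost is one table shell, one footnote, a derivation sentence and a longer table of two or three dose blocks. Solicited symptoms are already recorded daily, so no new data are needed.
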